 - ❖ Planned elective surgery unrelated to the patient's diagnosis of multiple myeloma, such as hernia repair, may be allowed, at the discretion of the principle investigator, as long as it was performed at least 2 weeks prior to starting cabozantinib, and patients have recovered fully from this procedure
15. HIV seropositive patients with acceptable organ function who meet the patient selection criteria, and who are not on combination antiretroviral therapy, and whose absolute CD4⁺ count is ≥ 400 cells per cubic millimeter of blood, will be eligible. However, HIV positive patients on combination antiretroviral therapy will be ineligible, because of the potential for pharmacokinetic interactions with cabozantinib.

16. Screen subjects prior to treatment whose baseline hepatitis B serologic status is unknown. Subjects, who are chronic carriers of hepatitis B virus, please screen with hepatitis B DNA to exclude active viral replication and monitor hepatitis B DNA at regular intervals while on study.
17. Sexually active subjects (men and women) must agree to use medically accepted barrier methods of contraception (eg, male or female condom) during the course of the study and for 4 months after the last dose of study drug(s), even if oral contraceptives are also used. All subjects of reproductive potential must agree to use both a barrier method and a second method of birth control during the course of the study and for 4 months after the last dose of study drug(s). **Male subjects must agree to not donate sperm for at least 90 days after the last dose of Carfilzomib.**

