3.2 EXCLUSION CRITERIA

1. Patients who are receiving any concurrent investigational agent with known or suspected activity against multiple myeloma, or those whose adverse events due to agents administered more than 4 weeks earlier have not recovered to a severity of grade 0 or grade 1.
2. Patients who have known central nervous system involvement with multiple myeloma will be excluded from this clinical trial because of their poor prognosis and because they often develop progressive neurologic dysfunction that would confound the evaluation of neurologic and other adverse events.
3. Patients who have previously been treated with another agent targeting the *MUC20/c-Met* axis, including either monoclonal antibodies to *MUC20* or c-Met, or small molecule inhibitors of c-Met.
4. Patients with a known history of allergic reactions attributed to compounds of similar chemical or biologic composition to cabozantinib.
5. Cabozantinib is metabolized by CYP3A4. The metabolism and consequently overall pharmacokinetics of cabozantinib could be altered by inhibitors and/or inducers or other substrates of CYP3A4. It is recommended that chronic concomitant treatment with strong

CYP3A4 inhibitors (eg, phenytoin, carbamazepine, rifampin, rifabutin, rifapentine, phenobarbital, and St. John's Wort) or inducers should be avoided because it may significantly decrease cabozantinib concentrations. If patients are taking any strong CYP3A4 inhibitors, alternate medications with no or minimal CYP3A4 inhibitors should be sought prior to trial enrolment. While mild inhibitors/inducers of these cytochrome P450 isoenzymes are not specifically excluded, investigators should be aware that cabozantinib exposure may be altered by the concomitant administration of these drugs, and avoidance is also recommended. Lists including medications and substances known or with the potential to interact with CYP3A4 are provided in Appendix G.

6. Uncontrolled or ongoing/active infection. Due to side effect profile of cabozantinib, patients with the following history will also not be eligible for the trial: patients with a recent history of hemorrhage or hemoptysis; patients with dehiscence or wound healing complications requiring medical intervention; patients with severe hypertension that cannot be controlled (blood pressure of > 150 systolic or > 100 diastolic mmHg) with anti-hypertensive therapy within 7 days of first dose of therapy.

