5.3.4 CONCOMITANT MEDICATIONS TO AVOID IF POSSIBLE

The following therapies *should be avoided* if possible, while the subject is on study:

- Palliative external radiation to bone metastasis for bone pain should not be performed while on study. Subjects who have such an intervention may be considered not evaluable (and may be assigned a censoring or progression date) for certain efficacy endpoints;
- Chronic co-administration of cabozantinib with strong inducers of the CYP3A4 family (eg, phenytoin, carbamazepine, rifampin, rifabutin, rifapentine, phenobarbital, and St. John's Wort) may significantly decrease cabozantinib concentrations and should be avoided. Selection of alternate concomitant medications with no or minimal CYP3A4 enzyme induction potential is recommended;
- Caution must be used when discontinuing treatment with a strong CYP3A4 inducer in a subject who has been concurrently receiving a stable dose of cabozantinib, because this could significantly increase the exposure to cabozantinib;
- Co-administration of cabozantinib with strong inhibitors of the CYP3A4 family (eg, ketoconazole, itraconazole, clarithromycin, indinavir, nefazodone, nelfinavir, and ritonavir) may increase cabozantinib concentrations and should be avoided. Grapefruit and Seville oranges may also increase plasma concentrations of cabozantinib and should be avoided.

Additional information on potential drug interactions with cabozantinib is provided in Section 5.3.5.

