5.3.5 Potential for Drug Interactions

Cytochrome P450 (CYP): Data from a clinical drug interaction study (Study XL184-008) show that clinically relevant steady-state concentrations of cabozantinib appear to have no marked effect on the area under the plasma drug concentration time curve (AUC) of co-administered rosiglitazone, a CYP2C8 substrate. Therefore, cabozantinib is not anticipated to markedly inhibit CYP2C8 in the clinic, and by inference, is not anticipated to markedly inhibit other CYP450 isozymes that have lower [I]/Ki values compared with CYP2C8 (ie, CYP2C9, CYP2C19, CYP2D6, CYP1A2, and CYP3A4). In vitro data indicate that cabozantinib is unlikely to induce cytochrome P450 enzymes, except for possible induction of CYP1A1 at high cabozantinib concentrations (30 μ M).

Cabozantinib is a CYP3A4 substrate and a weak substrate for CYP2C9 (but not a CYP2D6, CYP2C8, CYP2C19, CYP2B6, or CYP1A2 substrate), based on data from in vitro studies. Results from a clinical pharmacology study, XL184-006, showed that concurrent administration of cabozantinib with the strong CYP3A4 inducer, rifampin, resulted in an approximately 77% reduction in cabozantinib exposure (AUC values) after a single dose of cabozantinib in healthy volunteers. Chronic co-administration of cabozantinib with strong inducers of the CYP3A4 family (eg, phenytoin, carbamazepine, rifampin, rifabutin, rifapentine, phenobarbital, and St. John's Wort) may significantly decrease cabozantinib concentrations. The chronic use of strong CYP3A4 inducers should be avoided. Other drugs that induce CYP3A4 should be used with caution because these drugs have the potential to decrease exposure (AUC) to cabozantinib. Selection of alternate concomitant medications with no or minimal CYP3A4 enzyme induction potential is recommended.

Results from a clinical pharmacology study, XL184-007, showed that concurrent administration of cabozantinib with the strong CYP3A4 inhibitor, ketoconazole, resulted in a 38% increase in

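### Exclusion 5 calls seven strong CYP3A4 inducers inhibitors and only recommends avoiding them, so a patient who stays on a strong inducer or inhibitor is not clearly barred from the 3+3 phase

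*Combined protocol and SAP*

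**What the plan says.** Section 3.2, exclusion 5, recommends against chronic use of strong "CYP3A4 inhibitors (eg, phenytoin, carbamazepine, rifampin, rifabutin, rifapentine, phenobarbital" and St. John's Wort. It then adds inducers, and gives lower cabozantinib concentrations as the reason. Its one instruction for a patient already on such a drug is: "If patients are taking any strong CYP3A4 inhibitors, alternate medications with no or minimal CYP3A4 inhibitors should be sought prior to trial enrolment". It continues: "While mild inhibitors/inducers of these cytochrome P450 isoenzymes are not specifically excluded". For lists it points to Appendix G. Appendix A, exclusion 5, repeats this text on a form where every exclusion must be answered no.

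Section 5.3.4 gives the same seven drugs their correct class: "strong inducers of the CYP3A4 family (eg, phenytoin, carbamazepine, rifampin, rifabutin, rifapentine, phenobarbital" and St. John's Wort. It lists strong inhibitors separately (ketoconazole, itraconazole, clarithromycin, indinavir, nefazodone, nelfinavir, ritonavir) and says they may raise exposure. Its heading asks only for avoidance where possible, and it also advises: "Caution must be used when discontinuing treatment with a strong CYP3A4 inducer in a subject who has been concurrently receiving a stable dose" of cabozantinib.

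Inclusion 15 in Section 3.1 handles a related problem with a firm rule: "HIV positive patients on combination antiretroviral therapy will be ineligible, because of the potential for pharmacokinetic interactions with cabozantinib".

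**The concern.** There are two faults.

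- **The drug classes are wrong.** All seven examples offered as inhibitors are inducers. The item names no true inhibitor, does not say that inhibitors raise exposure, and directs sites to seek alternatives for inhibitors only.
- **There is no condition to answer.** The item recommends and advises. It does not say what happens to a patient who cannot change the drug, so two sites could tick the same patient differently. The remark about mild agents suggests that strong agents were meant to be excluded, but no sentence does so.

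This matters most in phase I. Sections 5.7 and 10.2 settle each dose level on 3 to 6 patients and on DLTs in cycle 1. A patient on a strong inducer contributes a full observation at the nominal dose while being exposed to far less. If the inducer is later stopped, exposure rises sharply with no change in dose. A strong inhibitor works the other way and is mainly an avoidable safety risk for that patient.

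**Working it through.** The plan states no figure on this point, so there is none to reproduce. The check has a textual part and two illustrations of size.

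**1. Classification.** The seven drugs are phenytoin, carbamazepine, rifampin, rifabutin, rifapentine, phenobarbital and St. John's Wort. Exclusion 5 and Appendix A call them inhibitors. Sections 5.3.4 and 5.3.5 and the inducer table in Appendix G list all seven as inducers. None is in the Section 5.3.4 list of strong inhibitors. Seven of seven are therefore mislabelled.

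**2. Exposure.** Section 5.3.5 reports that rifampin "resulted in an approximately 77% reduction in cabozantinib exposure (AUC values") and that the "strong CYP3A4 inhibitor, ketoconazole, resulted in a 38% increase in" exposure. Both come from single doses in healthy volunteers. I assume that exposure is proportional to dose and that these ratios carry over to patients.

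| Nominal dose | With strong inducer (× 0.23) | With strong inhibitor (× 1.38) |
|---|---|---|
| 20 mg | 4.6 mg | 27.6 mg |
| 40 mg | 9.2 mg | 55.2 mg |
| 60 mg | 13.8 mg | 82.8 mg |

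Under induction, 60 mg falls below the lowest level of 20 mg. Stopping the inducer multiplies exposure by 1/0.23 = 4.35. The inhibitor shift of 1.38-fold is smaller than either dose step (40/20 = 2-fold, 60/40 = 1.5-fold).

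**3. Chance that a level clears.** I take a level to clear with 0/3 DLTs, or with 1/3 and then 0/3. The documents give no DLT rates, so the rates below are assumptions.

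- Three ordinary patients with DLT rate p: P = (1−p)³ + 3p(1−p)²(1−p)³.
- One of the first three has DLT rate q instead: P = (1−q)(1−p)² + [q(1−p)² + 2p(1−p)(1−q)](1−p)³.

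One inducer patient at 60 mg:

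| p | No inducer patient | q = 0.10 | q = 0 | Rise (points) |
|---|---|---|---|---|
| 0.33 | 0.434 | 0.537 | 0.582 | 10 to 15 |
| 0.40 | 0.309 | 0.425 | 0.464 | 12 to 15 |
| 0.50 | 0.172 | 0.284 | 0.313 | 11 to 14 |

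Worked line for p = 0.40, q = 0.10: 0.9 × 0.36 + [0.1 × 0.36 + 2 × 0.4 × 0.6 × 0.9] × 0.216 = 0.324 + 0.468 × 0.216 = 0.425.

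Section 10.2 can also be read literally, so that 1/3 already stops a level and only 0/3 clears. The rise is again about 10 to 15 points: at p = 0.33 from 0.30 to 0.40–0.45, and at p = 0.50 from 0.125 to 0.225–0.25.

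One inhibitor patient at 40 mg lowers the chance of clearing by 4 to 7 points:

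- p = 0.15, q = 0.25: 0.814 to 0.770
- p = 0.20, q = 0.30: 0.709 to 0.661
- p = 0.25, q = 0.40: 0.600 to 0.527

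**The case against.** The strongest reply is that this is a drafting slip with little expected effect.

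- **The mislabel admits nobody.** This stands. The sentence goes on to name inducers, states their effect correctly, and refers to a correct appendix.
- **A sensible site would treat strong agents as excluded.** The item sits among the exclusions, and only mild agents are said not to be excluded. That is a fair reading of intent, but it remains an inference.
- **Other safeguards exist.** Concomitant drugs are taken at screening, recorded from 28 days before first dose, and reviewed on cycle 1 day 1 (Sections 5.2.1, 5.3.2, 5.2.2). The lead site confirms eligibility (4.2), the Principal Investigator is to be alerted to interacting drugs (2.2.2), and exclusion 13 allows judgment. Section 5.3.5 advises avoidance without the softer heading of 5.3.4. These steps make an affected patient visible. They do not say what to decide, and central confirmation is made against the same unclear item.
- **Section 5.3.4 concerns drugs on study, not at entry.** This is partly right: the inducer could have been started on study, and the caution about stopping it is a useful warning. It still shows that concurrent use was foreseen.
- **Later toxicity informs the phase II dose.** Section 10.1 says so, which gives a chance of correction. It does not change how the level was cleared.
- **The 10 to 15 points are conditional and generous.** This stands. The patient still receives carfilzomib and dexamethasone, so a DLT risk of zero is optimistic; at q = 0.20 the rise is 6 to 8 points. If 1% to 5% of candidates used such a drug (an assumption), the chance of at least one in the first three is 1 − 0.99³ = 3% to 1 − 0.95³ = 14%. The average shift is then about 0.3 to 2 points, even taking the 10 to 15.
- **The checklist lets a formally ineligible patient be admitted with a stated reason.** True, but a firm criterion would at least require that reason to be recorded.

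**Conclusion.** The concern holds. The misclassification is a plain error in an operative criterion and its checklist copy, and no sentence makes a patient who remains on a strong CYP3A4 agent ineligible. For an affected patient on a strong inducer the effect is large: about a 4.3-fold loss of exposure, on single-dose healthy-volunteer data and assumed proportionality. For a cohort containing one such patient, the chance of clearing 60 mg rises by 10 to 15 points if that patient's DLT risk is 0 to 10% and the true rate is 33% to 50%. The effect of an inhibitor is smaller. Averaged over the trial, the effect depends on how often such drugs are used, which the documents do not say, and it may be small. The point bears on patient safety and on the MTD decision. No effect on the response rate is claimed. It should be fixed, but it does not undermine the design.

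**What to change.** In exclusion 5 and Appendix A item 5:

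- Move the seven drugs under strong inducers, with decreased exposure as the effect.
- Name the strong inhibitors from Section 5.3.4, with increased exposure as the effect.
- Apply the instruction to seek alternatives to both classes.
- State the criterion as a yes/no exclusion in the manner of inclusion 15: chronic use of a strong CYP3A4 inhibitor or inducer not stopped before the first dose, with the interval set by the sponsor. This should apply at least to phase I.

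The cost is a wording amendment to one criterion and one checklist line, and the loss of a few patients who cannot change such a drug.

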3.3 INCLUSION OF WOMEN AND MINORITIES

Both men and women of all races and ethnic groups are eligible for this trial. Accrual targets for men and women, as well as for various ethnic categories, are up to 32 subjects to obtain 17 evaluable subjects.

4. REGISTRATION PROCEDURES

4.1 Recruitment

Subjects who are referred to the Nebraska Medical Center (NMC) / UNMC, or other IRB approved participating sites (MD Anderson), with relapsed and refractory (RR) multiple myeloma (MM) who have lost response to carfilzomib may be eligible for this study.

Screening eligibility based on standard clinical care will be performed by the treating physician at the time of encounter. On initial presentation assessment of ECOG performance Status will be completed.

After offering consent, the patient's primary Oncologist will make the decision as to screened eligibility of the candidate based on the eligibility criteria listed above. If the patient is screened as potentially eligible, he/she will then be offered the option to participate. An informed consent will be signed by the patient after thorough review of the study is completed by the physician and his/her designee.

Some insurance carrier's may decline to cover the costs of usual medical care if the patient is participating in a clinical trial. The patient will be provided assistance by the research nurse coordinator or designated staff in determining if the insurance carrier will decline coverage. Insurance carriers may or may not pay for study related expenses. The patient can then decide if they wish to participate.

4.2 Eligibility Verification/Registration:

Before patients are registered to the study, an eligibility checklist (Appendix A) must be completed to verify the subject meets the eligibility criteria. Informed consent must be obtained by following procedures defined in section 12.6 entitled Process of Informed Consent.

Subjects will be registered through the sponsor PI by contacting the UNMC Fred & Pamela Buffett Cancer Center Research Project Coordinator.

All Study personnel from UNMC and non-UNMC IRB approved sites will contact the UNMC Research Project Coordinator if a patient appears to meet the eligibility criteria. They will email or fax the completed eligibility checklist (Appendix A). The Eligibility Check list will be

maintained in a study file. If the UNMC Multi-site Project Manager confirms that the subject meets criteria and target accrual has not been met, approval for the subject will be given. A confirmation of Registration will be forwarded by the UNMC Multi-site Project Manager.

In the event of an after-hours potential enrollment (i.e., clinic coast time differences), or an immediate need-to-treat based on potential subject condition, registration can be accomplished by contacting the sponsor PI [name], MD directly by email: [contact] (response required) or by phone/[contact] or [contact]. Additionally, the UNMC Research Project Coordinator must be notified in or to meet UNMC Protocol Review Monitoring System (PRMS) reporting requirements.

Participating/Collaborating Sites:

Participating/Collaborating sites must have both local *and* UNMC IRB approval, and have met all other UNMC criteria to enroll. Study personnel from non-UNMC IRB approved sites will provide the UNMC Multi-site Project Manager with the following information:

- Demographics fax/scan cover sheet (located in the Study Manual)
- Copy of the signed and dated consent form (subject signature obliterated with signature line and subject initials visible)
- Signed Eligibility Checklist

Registration Date: eligibility verification and notification of assigned subject number (by UNMC) will be known as the Registration date.

Date of enrollment: is defined as the date of the start of study treatment / first protocol related intervention.

The listed documents/ information for subjects enrolled will be provided to the PRMS office within one (1) week of enrollment as applicable:

- UNMC and Participating Site Protocol Numbers
- Investigator/Participating Site Identifier (ID)
- Subject ID: Assigned by UNMC [Site ID followed by subject number (##-##)]
- Consent Date: Date subject signed consent
- Patient demographics: gender, birth date (mm/dd/yyyy), race, ethnicity
- Re-consent Date: (If applicable)
- Ineligibility Status: (If known)
- Off Study Date: (If applicable)

4.3 Pathology Requirements

Pathology material will be reviewed, and the diagnosis confirmed by each site's Pathology department as outlined in protocol.

Additional bone marrow aspirate pathology material is required to be captured at screening and after cycle 2 for correlative studies. See Section 5.8 for details of the required samples.

4.4 Instructions for Patients Who Do Not Start Assigned Protocol Treatment

If a subject does not receive any assigned protocol treatment after consenting, baseline and

follow-up data will still need to be collected and submitted according to the instructions in the protocol. The reason he/she did not receive any treatment and the date and type of the first non-protocol treatment that the subject receives must also be reported.

4.5 Requirements for Submitting Regulatory Documents UNMC and Participating Institutions:

Before an institution may enroll patients, all site activation criteria must be met by submitting required protocol specific regulatory documents to the study project manager at UNMC Fred & Pamela Buffett Cancer Center.

4.6 Required Protocol Specific Regulatory Documents

1. Confirmation that the UNMC Team Designee(s) conducted an initial site teleconference prior to opening a protocol to accrual at the participating site.
2. Copy of IRB Informed Consent Document.

NOTE: Any deletion or substantive modification of information concerning risks or alternative procedures contained in the sample informed consent document must be justified in writing by the investigator and approved by the IRB.

3. Copy of each participating/collaborating site's IRB Approval Letter and current IRB Roster, Federal Wide Assurance (FWA) Number or IRB Statement of Compliance.

NOTE: The above submissions must include the following details:

- Full protocol title and number
- Version Date
- Type of review (full board vs. expedited)
- Date of review.
- Signature of IRB official

5. TREATMENT PLAN

5.1 AGENT ADMINISTRATION

The recommended starting daily dose of cabozantinib is 20 mg (one 20-mg capsules). It will not be administered with food. Patients will be instructed not to eat for at least 2 hours before and at least 1 hour after taking cabozantinib. Capsules will be swallowed as whole and will not be opened. Patients will be instructed to not take a missed dose within 12 hours of the next dose. cabozantinib will not be ingested with grapefruit, grapefruit juice or nutritional supplements that are known to inhibit cytochrome P45.

Treatment will be administered on an outpatient basis. Reported adverse events and potential risks are described in Section 9. Appropriate dose modifications are described in Section 5.7. No investigational or commercial agents or therapies other than those described below may be administered with the intent to treat the patient's malignancy.

To assess compliance with treatment, all patients will be requested to maintain a medication diary of each dose of medication. This medication diary will be returned to the research staff at the end of each cycle of therapy. A sample patient study medication diary is provided in Appendix H.

